## **8.2.3 Dose Reduction**

*All reductions of IMP dose must be documented on the appropriate page of the patient's CRF. Dose reduction may occur either during treatment cycles, or between cycles, as clinically indicated.*

In the event of Grade 3 treatment-related AEs that are self-limiting or manageable by supportive care or other therapy, the patient may continue in the study if there is evidence of OR, SD, or other clinical benefit, but must do so at a reduced dose of IMP. Patients may not be retreated until retreatment criteria are met (see [Section 6.7.1](#)).

### **8.2.3.1 Dose Reduction Schedule**

If toxicity is to be managed by dose reduction, the IMP dose will be decreased as follows ([Table 6](#), [Table 7](#)):

Table 6: Dose-Reduction of Sym004		
Sym004 Dose	First Reduction	Second Reduction
6 mg/kg	4.5 mg/kg	3 mg/kg

Abbreviations (in alphabetical order): kg, kilogram; mg, milligram

Note: Dose Reductions for 9 mg/kg loading dose NA; the number of dose reductions allowed is limited to 2 ([Appendix 7](#))

Table 7: Dose-Reduction of Futuximab and Modotuximab		
Futuximab or Modotuximab Dose	First Reduction	Second Reduction
3 mg/kg	1.5 mg/kg	Not applicable

Abbreviations (in alphabetical order): kg, kilogram; mg, milligram;

Note: Dose Reductions for 4.5 mg/kg loading dose NA; the number of dose reductions allowed is limited to 1

#### **8.2.4 Reescalation/Rechallenge Following Dose Reduction**

Once a patient has undergone a dose reduction, the patient will continue to be treated at the reduced dose throughout the remainder of their time on study treatment. There is no provision in this study for either reescalation to the previous dose or challenge with a higher dose of IMP.

## 9 DISCONTINUING PATIENTS FROM STUDY TREATMENT

Every reasonable effort will be made to keep patients in the study; however, if a patient is discontinued from study treatment, every effort will be made by the Investigator to complete and report the reasons for treatment discontinuation as thoroughly as possible. This includes EOT observations, as required by the protocol at the time of treatment discontinuation, or before initiation of a new treatment, whichever comes first, as well as 1M FUP evaluations (**Section 7**). The reason for treatment discontinuation must be clearly documented on the appropriate page of the CRF. A CRF must be completed for any patient who receives any amount of IMP.

### 9.1 Criteria for Treatment Discontinuation

Patients will be discontinued from further treatment with IMP in the event of any of the following:

1. Progressive Disease: Confirmed radiographically (and evaluated according to RECIST v1.1)

*Note: Patients receiving futuximab or modotuximab with documented PD at the EOC2 (or prior to the EOC2) will be offered the opportunity to crossover to receive Sym004 or will be discontinued from study.*

2. Clinical Progression: Treatment failure not meeting the criteria for PD, but considered by the Investigator to require treatment discontinuation (i.e., global deterioration characterized by worsening PS, weight loss, and/or worsening clinical symptoms). **Every effort will be made to obtain imaging studies at the time of clinical progression.**

3. Adverse Event including:

- Hepatotoxicity characterized by:
  - AST and/or ALT elevation  $> 3 \times$  ULN (or  $> 3 \times$  baseline if elevated at study entry due to hepatic involvement by tumor), with
  - total bilirubin  $\geq 2 \times$  ULN without initial findings of cholestasis (i.e., serum ALP  $< 2 \times$  ULN), and
  - No explanation for the above findings such as viral hepatic injury, preexisting or acute liver disease, or another drug or condition capable of causing the observed injury

*Adapted from: Hy's Law. Drug-induced liver injury: premarketing clinical evaluation. Guidance for Industry. U.S. Department of HHS, FDA, CDER, CBER, 2009*

- Any of the following AEs:
  - Need for more than 2 dose reductions (Arm A), or more than 1 dose reduction (Arm B or Arm C)
  - Grade 4 IRR
  - Grade 4 EGFR-associated dermatologic AE
  - Torsade de pointes arrhythmia or other life-threatening arrhythmias
- Any other AE or SAE considered by the Investigator to require treatment discontinuation

Note: AEs resulting in a patient's permanent discontinuation from study treatment, regardless of seriousness or relationship to IMP, MUST be reported promptly to the Sponsor (or designee).

In the event of Grade 3 treatment-related AEs that are self-limiting or manageable by supportive care or other therapy, the patient may continue in study if there is evidence of response, disease stabilization, or other clinical benefit, but must do so at a reduced dose of IMP (see **Section 8.2.3**). Patients may not be retreated until retreatment criteria are met (see **Section 6.7.1**).

4. **Physician Decision:** Includes any reason which in the opinion of the Investigator would justify treatment discontinuation (e.g., use/requirement for a non-permitted concomitant medication; requirement for a significant surgical procedure; intercurrent illness which would prevent completion of study-related evaluations)

Note: Patients requiring a minor surgical procedure (e.g., port placement, skin abscess drainage) may continue at the Investigator's discretion following discussion with the Sponsor's Medical Monitor(s). A brief interruption in therapy may be considered.

5. **Withdrawal by Patient:** Withdrawal of consent and election to discontinue treatment (patients may leave the study at any time for any reason if they wish to do so, without consequence)
6. **Protocol Deviation:** Significant deviation from the protocol or eligibility criteria; such patients will be considered for discontinuation only following discussion with the Medical Monitor(s)
7. Noncompliance with study procedures
8. Pregnancy
9. Lost to Follow-up
10. Death
11. Study Terminated by the Sponsor

## 9.2 Replacements

After randomization to the study, no patients will be replaced. Patients NE for antitumor activity assessment, as defined (**Section 3.2**), or patients discontinuing from study prior to the EOC2 due to either documented PD or for reasons other than documented PD, will not be replaced.

## 9.3 Criteria for Premature Discontinuation of the Trial

This trial may be prematurely discontinued in the event of, but not limited to, any of the following:

- New information leading to an unfavorable benefit-risk profile of the IMP, e.g., due to:
  - Evidence of lack of efficacy of the IMP
  - Occurrence of significant previously unanticipated AEs
  - Clinically significant increase in the frequency or severity of anticipated AEs
  - Other clinically important safety findings

Note: Evidence of lack of efficacy may arise from this trial or from other trials; unfavorable safety findings may arise from clinical or non-clinical examinations, e.g., toxicology.

- Sponsor's decision that continuation of the trial is unjustifiable for medical or ethical reasons
- Poor enrollment making completion of the trial within an acceptable time frame unlikely
- Discontinuation of development of the Sponsor's IMP
- Upon request of Health Authorities

Health Authorities and IRBs/ECs will be informed about the discontinuation of the trial in accordance with applicable regulations.

## 10 ADVERSE EVENTS

*(Instructions for reporting AEs/SAEs apply to any IMP being evaluated in this trial)*

### 10.1 Definitions of Adverse Events

#### 10.1.1 Adverse Event

An AE is any untoward medical occurrence in a patient or a clinical investigation subject administered a pharmaceutical product and which does not necessarily have a causal relationship with this treatment. An AE can therefore be any unfavorable and unintended sign (including an abnormal laboratory finding), symptom, or disease temporally associated with the use of an IMP, whether or not considered related to the IMP.

Causality for an AE will be assessed as related or not-related to IMP. Any AE, regardless of causality, that also meets the seriousness criteria, will be reported as an SAE.

#### 10.1.2 Events Not to be Considered as Adverse Events

A preexisting condition (i.e., a disorder that is present before the AE recording period starts and is noted on the medical history/physical examination form) should not be recorded as an AE unless the condition worsens or episodes increase in frequency during the AE recording period.

PD will not be captured as an AE as this will be recorded as part of the patient's efficacy evaluation. PD should be reported as an AE if the nature of the PD is different than expected (i.e., signs/symptoms are not typical of PD).

Note: PD may be reported as an AE in the case of patient death, with death being the outcome of the event.

An abnormal laboratory value or an abnormal physiological test finding (e.g., ECG) need not be reported as an AE unless one of the following applies:

- The Investigator considers the abnormality clinically significant
- The event meets the definition of an SAE
- The event requires an intervention
- The event results in an action taken with IMP (e.g., dose-delay and/or discontinuation)

Diagnostic and therapeutic non-invasive and invasive procedures, such as surgery, should not be recorded as AEs. A medical condition for which an unscheduled procedure was performed, should however be recorded if it meets the definition of an AE. For example, acute appendicitis should be recorded as the AE and not the appendectomy.

Procedures to support the treatment regimens, such as insertion of central venous catheters, etc., should not be recorded as AEs, unless the procedures result in complications.

#### 10.1.3 Adverse Events of Medical Interest

Not applicable

#### 10.1.4 Serious Adverse Events

An SAE is an AE that meets one or more of the following regulatory outcome criteria:

- **Results in death**

In the case of deaths, the event(s) leading to the death should be recorded and reported as SAE(s) with the outcome “Fatal”. The death itself will not be reported as an SAE, unless the cause of the death is unknown (e.g., in case of unexplained or sudden death)

- **Is life-threatening**

The term “life-threatening” refers to an event in which the patient is at immediate risk of death at the time of the event; it does not refer to an event which hypothetically might cause death if it was more severe

- **Requires inpatient hospitalization or prolongation of existing hospitalization**

- **Results in persistent or significant disability/incapacity**

A disability is defined as any substantial disruption of a person’s ability to conduct normal life functions.

- **Is a congenital anomaly/birth defect**

- **Is medically important**

Medical and scientific judgment must be exercised in deciding whether an AE is believed to be “medically important”. Medically important events may not be immediately life-threatening or result in death or hospitalization but may jeopardize the patient or may require intervention to prevent one of the other outcomes listed in this definition.

### 10.1.5 Events That Do Not Meet the Definition of Serious Adverse Events

PD will not be captured as an SAE unless the nature of the PD is different than expected (i.e., signs/symptoms that are not typical of PD).

Note: PD may be reported as an SAE in the case of patient death, with death being the outcome of the event.

Elective surgery or other scheduled hospitalization periods that were planned before the patient was included in this trial are not to be recorded as SAEs, unless an outcome of the surgery/hospitalization was considered serious.

Hospitalization for observation or convenience prior to or following IMP administration without an SAE occurring should not be recorded as an SAE, e.g., if a patient is hospitalized merely for observation, or if a patient begins or finalizes the infusion at a time of day requiring a convenience overnight stay in the hospital.

Procedures to support the treatment regimen that require hospitalization should not be recorded as SAEs; however, in cases where a procedure results in complications requiring/prolonging hospitalization, this must be recorded and reported as an SAE.

## 10.2 Adverse Event Recording and Reporting

All AEs will be recorded from signing of informed consent for participation in the trial. The recording period ends 30 days after receiving the final dose of IMP (at the time of the 1M FUP Visit), unless extended FUP is indicated, per the clinical trial protocol.

Note: Patients who sign informed consent and are subsequently deemed to be screen failures will be followed for the occurrence of SAEs/AEs until it is determined that they will not be participating in the trial.

### 10.2.1 Information to be Provided for Each AE

The Investigator must record all directly observed AEs and all AEs spontaneously reported by the patient. Information regarding the occurrence of AEs should be elicited through open-ended questioning of the patient, review of physical examination findings, and review of laboratory results or other safety information, e.g., ECGs.

All AEs that occur in patients during the AE recording period must be recorded/entered to the AE section of the CRF, whether or not the event is assessed as related to IMP. If the AE is serious, the SAE report forms must also be completed and submitted. Information to be provided for each AE term reported includes:

- **Diagnosis**

A diagnosis should be recorded, if possible. If no diagnosis is available, signs and symptoms should be recorded instead. For fatal AEs, death is an outcome of the AE. The cause of death (rather than the term “death”) should be recorded.

- **Severity**

The Investigator will use the CTCAE version 5\* to describe the severity of an AE. If the severity of an AE is not specifically graded by the CTCAE guidance document, the Investigator should use the general definitions of Grades 1 to 5 as per the following, and use his/her best medical judgment to describe the severity of the AE (**Appendix 3**):

- Grade 1: Mild
- Grade 2: Moderate
- Grade 3: Severe
- Grade 4: Life-threatening or disabling
- Grade 5: Death caused by the event

Changes in severity of AEs will be recorded.

Generally, an AE of CTCAE Grade 4 or 5 qualifies for SAE reporting to the Sponsor (or designee). However, a laboratory abnormality of Grade 4 does not need to be reported as an SAE, unless it meets one of the SAE criteria.

*\*See <[https://ctep.cancer.gov/protocoldevelopment/electronic\\_applications/ctc.htm#ctc\\_50](https://ctep.cancer.gov/protocoldevelopment/electronic_applications/ctc.htm#ctc_50)>*

- **Relationship to IMP/Causality**

The Investigator will attempt to assess causal relationship of the event to the IMP. Relatedness must be assessed and recorded within the initial report (CRF and SAE report form).

The causal relationship is an assessment of whether the event is related to the use of the IMP. It is not an evaluation of whether the event could hypothetically occur in the investigational patient population.

The causal relationship of an AE to the IMP will be rated using a 2-point causality scale (**Appendix 4**):

- Not-related
- Related

- **Outcome**

The outcome of the AE must be assessed by the Investigator utilizing one of the following options:

- Recovered/resolved
- Recovered/resolved with sequelae
- Recovering/resolving
- Not recovered/not resolved
- Fatal
- Unknown

Instructions for reporting changes in an ongoing AE during a patient's participation in the trial will be provided.

### **10.2.2 Required Follow-up for AEs**

Appropriate consultation and follow-up evaluations should be carried out until the event either resolves, returns to baseline status, or has been adequately explained and assessed by the Investigator as chronic and/or stable, and that no long-term deleterious effects have become evident.

This follow-up may extend beyond the 1M FUP Visit, to up to 4 months after the EOT if indicated, if the event has not resolved or been adequately explained.

Note: Patients who sign informed consent and are subsequently deemed to be screen failures will be followed for the occurrence of SAEs/AEs until it is determined that they will not be participating in the trial.

## **10.3 Serious Adverse Event Recording and Reporting**

### **10.3.1 Timeframes for Reporting to the Sponsor**

All SAEs occurring at any time from signing of informed consent for participation in the trial and until 30 days after receiving the final dose of IMP (at the time of the 1M FUP Visit) must be recorded on the SAE Report Form and recorded as an SAE in the CRF.

Note: Patients who sign informed consent and are subsequently deemed to be screen failures will be followed for the occurrence of SAEs/AEs until it is determined that they will not be participating in the trial.

In case of an SAE, the Investigator must, within 24 hours of awareness of the event, report the SAE to the Sponsor (or designee) by telefax or e-mail transmission. Fax number(s) and e-mail address(es) will be stated on the SAE Report Form and the SAE Report Form Completion Instructions. SAE follow-up information must also be reported to the Sponsor (or designee) within 24 hours of awareness.

SAEs, still ongoing after the 1M FUP Visit, should be followed on a regular basis according to the Investigator's clinical judgment, until the event resolves or until the Investigator assesses it as chronic or stable. The Sponsor (or designee) will pursue sufficient information and will return to the trial sites for such information as deemed required.

If the Investigator becomes aware of an SAE that occurred after the 1M FUP Visit and finds it to be related to the IMP (possibly-, probably-, or related to the IMP) or trial conduct, it must be recorded and reported to the Sponsor (or designee) as an SAE.

The Investigator should be aware of local reporting regulations to the IRB/EC. The Sponsor (or designee) will either supply the Investigator with the reports, which should be forwarded to the IRB/EC, or report directly to the IRB/EC depending on local regulations.

### **10.3.2 Safety Reporting to Health Authorities, IRBs/ECs, and Investigators**

Reportability of an SAE as a "Suspected Unexpected Serious Adverse Reaction" (SUSAR) will be determined solely by the Sponsor, based on seriousness, causality, and expectedness criteria.

In addition to SUSARs, the Sponsor or designee is responsible for reporting all relevant safety information regarding SUSARs, or other safety developments, to appropriate Health Authorities and central IRBs/ECs, as well as participating Investigators. Reporting of SUSARs to local IRBs/ECs will be handled either by the Sponsor or designee, or the Investigator depending on local regulations.

The timeline for notification of SUSARs is within 7 calendar days for fatal/life-threatening events and within 15 calendar days for all other SUSARs.

## **10.4 Pregnancy**

If any trial patient becomes pregnant during the trial, the patient must be discontinued from IMP immediately and the pregnancy must be reported to the Sponsor or designee according to the same timelines as an SAE. While pregnancy is not considered an AE, all pregnancies are tracked as SAEs within the safety database to follow-up on exposure to the fetus/infant.

Pregnancies reported in female partners of male trial patients must also be included in the safety database; therefore, a female partner of a male patient on the trial who becomes pregnant will be approached for consent to have the pregnancy followed until term and reported upon to the Sponsor (or designee).

All pregnancies must be followed up every third month and 1-month post-delivery to determine outcome and status of mother and child. Pregnancy complications and elective terminations for medical reasons must be reported as AEs or SAEs as appropriate. Elective terminations for non-medical reasons should be reported as follow-up, but not as a separate AE/SAE unless complications meet AE/SAE criteria. Spontaneous abortion must be reported as an SAE.

Any SAE occurring in association with a pregnancy brought to the Investigator's attention after the patient has completed the trial and considered by the Investigator as possibly-, probably-, or related to the IMP, must be promptly reported to the Sponsor (or designee).

All pregnancy information including follow-up information must be reported on a designated pregnancy form provided by the Sponsor (or designee).

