Disease Status and Safety Evaluation (screening)	
 
Disease status evaluation (imaging studies may be used to document tumor status at screening if performed within 14 days prior to 1st dose)
 
Safety evaluation (within 14 days prior to 1st dose unless otherwise stipulated)
 

Randomization Patients confirmed/authorized as fully eligible	
Treatment Assignment	
 
Randomization to Sym004 versus futuximab versus modotuximab (within 14-day screening window; CID1 dosing to occur ≤ 3 days (72 hours) after randomization)
 

Treatment Period	
Treatment	
 
C1D1 initial dose of IMP
 
28-day cycles until confirmed PD, unacceptable toxicity, or another discontinuation criterion is met
 
Tumor assessment at EOC2 with continuation of Sym004, or crossover to Sym004, as indicated
 
EOT visit within approximately 7 to 10 days following treatment discontinuation, or before initiation of a new treatment, whichever occurs first
 
1M FUP visit 30 days (+7 days) following last dose*
 
 
*Completion of the 1M FUP visit will be considered the end of study for the patient unless additional safety follow-up is required

Follow-up Period	
Post-Treatment Follow-up	
 
Safety FUP if an IMP-related AE has not resolved by the 1M FUP (2 months [4 months if necessary] following last administration of IMP)
 

Abbreviations (in alphabetical order): 1M FUP, 1-month follow-up; C1D1, Cycle 1 Day1; ctDNA, circulating tumor DNA; EOT, end of treatment; FUP, follow-up; ICF, informed consent form; PD, progressive disease; Q2M, every 2 months; Q2W, every 2 weeks

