Patients who received adjuvant chemotherapy and had documented recurrence (by imaging studies) during or within 6 calendar months of completion of the adjuvant chemotherapy are permitted to count the adjuvant therapy as one regimen of chemotherapy.

8. Patients with “acquired” resistance to commercially available anti-EGFR mAbs approved for the treatment of mCRC. Patients must have:
  - a. Received treatment with an anti-EGFR for >16 weeks
  - b. PD documented by imaging or clinical findings  $\leq$  6 calendar months after cessation of previous anti-EGFR mAb treatment
  - c. No more than 6 calendar months from last dose of previous anti-EGFR mAb treatment to date of consent for this trial (regardless of the line of therapy in which it was used)
9. Patients with an Eastern Cooperative Oncology Group (ECOG) performance status (PS) of 0 or 1 (or equivalent Karnofsky PS; [Appendix 1](#))
10. Patients, male and female, who are either not of childbearing potential or who agree to use a highly effective method of contraception during the study beginning within 2 weeks prior to the first dose and continuing until 3 months after the last dose of IMP.

Note: Women are considered of childbearing potential unless they have undergone hysterectomy and/or bilateral tubal ligation or oophorectomy, or have been postmenopausal for at least one year. Postmenopausal status in females under 55 years who have not been surgically sterilized should be

confirmed with a serum follicle-stimulating hormone (FSH) level within laboratory reference range for postmenopausal women.

A highly effective method of contraception is defined as non-hormonal contraception equivalent to a double-barrier method (includes a single-barrier method in combination with a spermicide) or intrauterine device (**Section 11.1**).

Women of childbearing potential (WOCBP) must have a negative pregnancy test within  $\leq 2$  working days prior to administration of the first dose of IMP.

11. Must have the ability to understand and give written informed consent for participation in this trial, including all evaluations and procedures as specified by this protocol

Note: Informed consent must be obtained prior to patient screening, and before any evaluations or procedures specifically related to this study are performed.

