#### 4.3.1 Patients to be Excluded

*(Patients must not meet any of the following criteria)*

1. Women who are pregnant or lactating or intending to become pregnant before, during, or within 3 months after the last dose of IMP. WOCBP, and fertile men with WOCBP-partner(s) not using and not willing to use a highly effective method of contraception.

Note: WOCBP includes any female who has experienced menarche and who has not undergone surgical sterilization (hysterectomy, bilateral tubal ligation, or bilateral oophorectomy), or is not postmenopausal. Post-menopause is defined as: 1) amenorrhea for  $> 12$  months with no other cause, or 2) irregular menstrual periods, on hormone replacement therapy (HRT), with a documented FSH level  $> 35$  mIU/mL.

WOCBP and fertile men will be informed as to the potential risk of procreation while participating in this trial. A pregnancy test will be performed, and the results reviewed, on each premenopausal WOCBP prior to first IMP administration. A negative pregnancy test performed within  $\leq 2$  working days prior to first IMP administration must be documented on the patient's case report form (CRF) (**Section 11.1**).

2. Patients with a prior history any of the following mutations in their tumor at the time of any previous assessment:
  - a. *RAS* (*KRAS* and *NRAS*) mutations in the following codons:
    - Exon 2: codon 12, 13
    - Exon 3: codon 59, 61
    - Exon 4: codon 117, 146
  - b. *BRAF* V600E mutation
  - c. *EGFR*-ECD V441D, V441G, S464L, G465E, G465R, S492R mutations
3. Patients with known, untreated central nervous system (CNS) or leptomeningeal metastases, or spinal cord compression; patients with any of these not controlled by prior

surgery or radiotherapy, or patients with symptoms suggesting CNS involvement for which treatment is required

Note: Patients with treated CNS metastases will be eligible if they are asymptomatic, do not require corticosteroids or anticonvulsants, and have confirmation of at least stable brain disease status as assessed by 2 imaging studies performed  $\geq 4$  weeks apart with the most recent performed within 4 weeks prior to first IMP administration.

Patients with newly identified CNS disease during study treatment will be considered to have PD and will be discontinued from treatment.

4. Patients with an active second malignancy or history of another malignancy within the last 5 years with the exception of:
  - a. Treated non-melanoma skin cancers

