## 11 PRECAUTIONS WHEN DOSING

### 11.1 Precautions Regarding Procreation

Studies have not been performed to determine whether Sym004, futuximab, or modotuximab affect reproductive function in males or can cause fetal harm. For this reason, men with partners of childbearing potential must use a highly effective method of contraception while receiving IMP. **“A highly effective method of contraception” is defined as non-hormonal contraception equivalent to a double-barrier method (includes a single-barrier method in combination with a spermicide) or intrauterine device.**

There have been no studies in pregnant females; therefore, it is not known whether Sym004, futuximab, or modotuximab can cause fetal harm when administered to a pregnant woman, or whether they can affect reproductive capacity. For this reason, WOCBP should only be administered IMP when highly effective contraceptive measures have been taken and when pregnancy tests are negative.

WOCBP includes any female who has experienced menarche and who has not undergone surgical sterilization (hysterectomy, bilateral tubal ligation, or bilateral oophorectomy), or is not postmenopausal. Post-menopause is defined as:

- Amenorrhea for  $\geq 12$  months with no other cause
- Irregular menstrual periods, on HRT, with documented FSH level  $> 35$  mIU/mL

Note: Women who are using oral contraceptives, other hormonal contraceptives (vaginal products, transdermal patches, or implanted or injectable products), or mechanical products such as an intrauterine device or barrier methods (diaphragm, condoms, spermicides) to prevent pregnancy, or are practicing abstinence, or where their partner is sterile (e.g., vasectomy), should be considered of childbearing potential.

Women and men of childbearing potential will be informed as to the unknown risk to procreation while participating in this trial and will be advised that they must use highly effective contraception within 2 weeks prior to the first dose and continuing until 3 months after final administration of IMP. A pregnancy test will be performed on each premenopausal female of childbearing potential within  $\leq 2$  working days prior to first IMP administration, and again at the end of the final treatment cycle.

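### Section 10.4 requires pregnancy reports only during the trial, which for a patient without extended safety follow-up ends about two months before the 3-month contraception period does

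*Protocol*

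**What the plan says.** Three sections fix a post-treatment contraception period. Inclusion criterion 10 (Section 4.2) asks male and female patients to use highly effective contraception "beginning within 2 weeks prior to the first dose and continuing until 3 months after the last dose of IMP". Exclusion criterion 1 (Section 4.3.1) rules out women "intending to become pregnant before, during, or within 3 months after the last dose of IMP". The last paragraph of Section 11.1 requires contraception of women and men, "continuing until 3 months after final administration of IMP". Section 11.1 gives the reason: the effect of these antibodies on a fetus is unknown.

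The reporting duty has a different end. Section 10.4 sets it as follows: "If any trial patient becomes pregnant during the trial, the patient must be discontinued from IMP immediately and the pregnancy must be reported". A partner is approached for consent if the male patient is on the trial. The footnote to Table 2 (Section 3.2) says: "Completion of the 1M FUP visit will be considered the end of study for the patient", with an exception where further safety follow-up is needed. That visit falls 30 (+7) days after the last dose. Section 6.2.2 ends the trial as a whole no later than 30 (+7) days after the last patient stops study drug.

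After completion, Section 10.4 covers "Any SAE occurring in association with a pregnancy brought to the Investigator's attention after the patient has completed the trial", and only if the investigator considers the SAE possibly, probably or definitely related. Section 10.3.1 likewise covers late SAEs related to the study drug or to trial conduct. Section 10.4 says that a pregnancy is not itself an AE.

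**The concern.** The protocol treats the 3 months after the last dose as a period in which conception should be avoided because fetal harm cannot be excluded. Reporting a pregnancy and following its outcome is how the sponsor would learn whether harm occurred. If the duty to report ends before the precaution does, an exposure that the protocol itself regards as relevant can go unrecorded. What remains reportable is selected: late events come in when they are already serious and judged related, while an uncomplicated pregnancy, or one whose outcome is not yet known, does not. Such a collection cannot show how often exposed pregnancies end normally.

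The point bears on what is left of the trial. Amendment 5 drops efficacy and keeps only clinical safety evaluation, and Sections 10.4 and 11.1 stay in force. Section 2.4 describes this as the first clinical study of the two antibodies as single agents, and one of the two treated patients received single-agent futuximab in Cycle 1 (Section 6.5.4).

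**Working it through.** The plan gives no figure of its own here, so the check is a comparison of days.

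**Inputs**
- End of the contraception period: 3 months after the last dose (4.2, 4.3.1, 11.1), taken as 90 to 92 days.
- End of study for the patient: the 1-month follow-up visit, day 30 to day 37 after the last dose (Table 2).
- Start of contraception: within 2 weeks before the first dose (4.2, 11.1), taken as 14 days.
- Length of treatment, for the whole-period share only: 12 weeks = 84 days. This is an assumption, borrowed from the average participation estimated in Appendix 9.
- Extended safety follow-up where a related AE persists: about 2 months, repeatable at 4 months (Table 2, Section 6.8), taken as 61 and 122 days.

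**Step 1. Days without a reporting duty** = end of contraception period − end of study for the patient.
- Smallest: 90 − 37 = 53 days.
- Largest: 92 − 30 = 62 days.

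**Step 2. Share of the 3-month post-dose period**
- 53 / 90 = 59%.
- 62 / 92 = 67%.

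**Step 3. Share of the whole contraception period** (3 months = 91 days)
- Whole period: 14 + 84 + 91 = 189 days.
- (91 − 37) / 189 = 54 / 189 = 29%.
- (91 − 30) / 189 = 61 / 189 = 32%.

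**Step 4. Patients in extended safety follow-up**
- Follow-up to 2 months: 91 − 61 = 30 days; 30 / 91 = 33% of the post-dose period.
- Follow-up to 4 months: 122 > 91, so no gap.

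**Step 5. Does another clause fill the gap?** For a pregnancy conceived on, say, day 60 in a patient who finished at the 1-month visit:
- The main trigger in 10.4 is not met, because the patient's study has ended.
- The post-completion clauses in 10.4 and 10.3.1 need a related SAE. An uncomplicated pregnancy is not an AE, so neither applies.
- Scheduled testing would not find it. The last planned pregnancy test is at end of treatment (Section 7.2.7.6, Table 4), with none at the 1-month visit.

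No duty to report this pregnancy arises, and so none to follow its outcome.

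**The case against.** The other side has five arguments.

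*The phrase is undefined.* Section 10.4 does not say whether *during the trial* refers to the patient or to the trial. The patient-level reading is an inference, but the same section speaks of what happens after a patient has completed the trial, and Table 2 defines that point. On the trial-level reading the last patient to stop treatment still has the full gap, because Section 6.2.2 closes the trial within 37 days.

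*Late pregnancies are not simply lost.* A reader might infer that nothing is collected after the 1-month visit. The documents do not support that. Related SAEs stay reportable, a birth defect meets a seriousness criterion (10.1.4), and the sentence requiring reported partner pregnancies to enter the safety database has no time limit. Only the approach for consent is tied to the male patient being on the trial. What stands is that a pregnancy without a related SAE is not required to be reported. The instruction to follow up all pregnancies governs those that reach the site; it does not lengthen the trigger.

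*The share depends on the denominator.* A reader might infer that most of the protocol's whole risk period is uncovered. That holds for the post-dose segment (59% to 67%), not for the full contraception period (about 30%), and extended follow-up shrinks or removes the gap.

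*Exposure is probably short.* Section 2.4.2 gives a Sym004 half-life of about 3 days after 12 mg/kg and 5 days after 18 mg/kg, so 30 days is about 10 or 6 half-lives (30/3, 30/5). Section 2.3 reports a longer half-life and accumulation for the single antibodies in monkeys, but both patients have been moved to or started on Sym004. This lowers the importance; it does not explain why the two periods differ.

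*Men.* A reader might infer a flat contradiction in Section 11.1, which first says "men with partners of childbearing potential must use a highly effective method of contraception while receiving IMP" and later gives 3 months. The first statement names no end after dosing, so the two can be read together. This supports only a request to reconcile the wording.

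**Conclusion.** The mismatch holds in the current text. For a patient without extended safety follow-up, a pregnancy conceived after the 1-month visit and within 3 months of the last dose carries no reporting duty unless a related SAE is attached to it. The gap lasts about 53 to 62 days: 59% to 67% of the post-dose contraception period, and about 30% of the whole contraception period on an assumed 12 weeks of treatment. It rests on the patient-level reading of *during the trial*; on the trial-level reading it remains for the last patient.

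These are day counts, not a risk estimate. Two patients are treated, accrual has stopped (Sections 4.1 and 6.2.3), and the documents do not say whether either patient, or a partner, is of childbearing potential. The expected number of affected pregnancies is therefore very small. This is a cheap improvement to safety reporting and does not threaten the trial's conclusions.

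**What to change.** In Section 10.4, keep the present start of the reporting period and move only its end, for example: *during the trial and until the end of the post-treatment contraception period stated in Section 11.1*. Apply this to pregnancies in patients and in partners, with the outcome follow-up that 10.4 already sets out. The start should not be reset to the first dose, because the present wording can cover a conception shortly before dosing that the pregnancy test missed.

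State in the same place that this passive duty continues beyond the end-of-study definition in Table 2 and the end-of-trial definition in 6.2.2, so that the passages do not conflict. Have the site remind the patient at the 1-month visit to report a pregnancy in that period. Reconcile the statements on men's contraception in Section 11.1 with each other and with inclusion criterion 10.

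The cost is a few sentences by amendment and a reminder at an existing visit, with no added visit or test. The downside is that the site keeps a passive reporting duty for about two further months per patient, running past formal trial closure for the last one.
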